## 5 Management activities & Code of conduct

#### 5.1 Contact with end users along the experimentation

In order to create a safe and inclusive environment for all end users (including control group), they will be allowed to contact the researcher in any moment for asking information and/or assistance. They will be treated fairly, fully informed about the reasons why questionnaires are asked and the purpose of the research, and updated about the ongoing of the project.

At this purpose, the researcher will be in contact daily with the participants. Even if this risk of technology dependency is present, however, technology has not yet achieved the level of sophistication required for natural human-robot interaction. At the moment, in fact, there is limited progress in the development of social robots capable of minimal and limited social interaction involving emotional, and psychological engagement with users under controlled conditions. Nevertheless, adjustments required to use safely social robots in emotional, social and psychological terms avoiding future addition towards them should be applied, as the provision of adequate training and daily support/monitoring of the researcher.

Finally, if after the experimentation, the participants would ask for a longer use of the system, they will be asked to be involved in similar studies to assure the continuity of use of the technology. Moreover, after the end of the study, the opportunity of receiving a personalized support on everyday technology will be offered to the participants, about eHealth literacy and similar solutions for health.

#### 5.2 Technical support and assistance

Each pilot site will guarantee the technical support on site. The technical support can be delivered in the following ways, depending on the nature of the issue:

- Remote support (phone calls, video-calls);
- On-site support when remote support is not successful.

In case end user partners cannot solve the issue, they can ask technical partners for support. On this purpose, a WhatsApp group with both end user and technical partner members will be created to quickly tackle the problem, as well as increasing knowledge on risks, issues, and solutions among all the partners.

Any participant will receive a handbook with instructions on how to use the system and to tackle recurring issues.

#### 5.3 Risk-benefit analysis and exit strategy

This study poses little risk to participants however, there are some risks. There is a risk that the elderly person may wish to stop interacting with the technological devices (for example because they do not like the robot). In this case the experiment will be immediately stopped and terminated.

To protect the safety of participants:

- Participants will be informed about the appropriate use of the devices (especially the social robot);
- The researcher will train the participant in the use of the devices and be available in case of problems;

• The technological devices (tablet and mobile connection) will be placed in the participant's home in a configuration that allows them to be used safely.

In the event of adverse events occurring despite the precautions described above (section 5.2):

- Participants will be instructed to press the "off" button on the device or to disconnect it according to the instructions in the user manual;
- Participants will call the researcher, who will assist the participant in case of problems.
- Participants will be able to call the researcher, who will come and ensure that no damage has been caused to the participants or to any other person.

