## 3 Field trial

#### 3.1 Study design

The field trial will be conducted as a controlled longitudinal study, with a before and after design where the observations are made on a series of enrolled individuals, receiving the intervention described below with control group, with data collected before and after the installation and use of the technical solution. The goal of trial evaluation is to assess the engAGE technology integration into everyday life, effectiveness on mitigating the cognitive decline, acceptance over six months, security and reliability of proposed solutions as well as the business perspective reflecting the market demand (including the willingness to pay) for the developed services. The field trial procedure will be divided into two different phases, after the recruitment of the participants: Baseline evaluation (T0, M1) and Final evaluation (T1, M6), with the aim of collecting data as follows:

- **Recruitment phase** (R): the recruitment protocol will include general information on the subjects, in particular, health status and cognitive condition. The information will be collected with the help of the caregiver/family member if needed.
- **Baseline evaluation** (T0, M1): that will consist of the first real contact with the users and their families, before the start of the field trial.
- **Mid-term evaluation** (T1, M3): the aim of mid-term evaluation is to collect useful information on the use of the engAGE platform after a short period of use for detecting and analysing the technology acceptance and usability issues.
- Final evaluation (T2, after six months of use, M6): the aim of this phase is to collect useful information on the whole benefits perceived by the users after a meaningful period of use of the system. The final evaluation will be conducted after the system de-installation, to detect and analyse the impact of the system in the daily life of the older people and their family. Moreover, the final evaluation aims to gain knowledge on elderly technology acceptance and usability issues to be compared with mid-term results (T1), in order to assess the longterm acceptance and provide methodological approach for further studies in the field.

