The **Reisberg Scale** [2] consists of 7 major clinical stages. It is used by clinicians and in care settings, but may be especially helpful for caregivers, as it is noticeably detailed regarding the general abilities of an individual at each stage and provides information about what to expect at different stages. The scores go from no cognitive decline (1) to very severe cognitive decline (7), through stages 2, 3, and 4 that are respectively: Very mild cognitive decline (age-associated memory impairment), mild cognitive impairment, and moderate cognitive decline.

The **4-items Geriatric Depression Scale (GDS)** [3] is a 4-items scale whose answers are yes or no. If all the items are answered negatively then the depression is excluded; if only one item is answered positively then the situation is uncertain; if at least 2 items are answered positively, the patient is depressed. Thus, this scale is easy and quick, and very useful in excluding depression.

The **Memory Assessment Clinics – Questionnaire (MAC-Q)** [4] is a 6-item scale that uses a 5-item Likert scale from "much better now"=1 to "much worse now"=5, and the last question scores double. The questionnaire asks the person to compare his or her memory with a previous period to measure age-related memory decline. Five items address specific situations frequently reported as problematic by those who experience memory loss with age. One item is a global item assessing general memory decline. A cutoff of 25 points or more indicates that the individual has a memory disorder.

**Clinical Frailty Scale (CFS).** [5] This descriptive scale divides the older participants into 9 classes based on the information provided by them and their relatives: between 1 and 3 the patient is non-frail, pre-frail if 4, he is frail from 5 to 9.

The **UCLA scale** [10] is a 20-item scale designed to measure one's subjective feelings of loneliness as well as feelings of social isolation. Participants rate each item as either O ("I often feel this way"), S ("I sometimes feel this way"), R ("I rarely feel this way"), N ("I never feel this way").

**EQ Visual Analogue Scale (EQ VAS)** [11] records the respondent's self-rated health on a 20 cm vertical, visual analogue scale with end-points labelled 'the best health you can imagine' and 'the worst health you can imagine'. This information can be used as a quantitative measure of health as judged by the individual respondents.

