#### 3.6 Description of the intervention

In this section, the intervention is descripted in details.

The experimental group (EG) use the engAGE system in two different settings: at healthcare organization and at home. At the healthcare organization, the primary end user (SMCI) interacts with Pepper. The interaction **at healthcare organization** is supervised by tertiary end users (formal caregivers, i.e., occupational therapist, psychologist, nurse, etc...) and includes the following activities: dialoguing with the robot, storytelling, drama play, cognitive and physical games. This interaction is planned to last about **1 hour and to be scheduled twice a week for 6 months**. **At his/her home**, the older user interacts with the tablet and is supervised by the relative informal caregiver. Also in this case, the user plays cognitive and physical games installed on MEMAS app. Even this activity is **performed for 0,5 hour, every day for 6 months**. Throughout the whole period of experimentation (unless (s)he decides otherwise), the older user wears the smartwatch that measures his/her physiological parameters and the steps. Any activity performed by the seniors is assigned by formal caregiver and can be personalized taking into account the user's abilities (difficulty levels of the games), lifestyle (reminding and monitoring services), and social interactions.

The activities performed by the user through the engAGE system are schematized in the figure below:

Figure 3. Summary of engAGE activities

Table 7. Games of the Engage platform

Name of games	Description
	Familiar games

Crossword	Helps with long term memory, having	★: easy level (infinite tips)			
	definition or pictures.	★★: medium level (limited tips)			
Karaoke	Helps SMCI to have fun while singing songs they already know (train memory without noticing).	★★★: hard level (no tips)			
Memory card	Helps with spatial memory, which can help SMCI to find lost objects in the future.				
Sudoku	Helps with visual memory, using numbers instead of letters can be easier and more enjoyable. It's an appreciated game for SMCI.				
2 differences game	Helps to stay focus, observe, retain the information to seek.				
Quizzes					
Picture quiz	Find the celebrities/animals behind.				
	$\star$ : picture $\star$ $\star$ : pixelated photo $\star$ $\star$ $\star$ :	★: silhouette			

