#### 4.2 Risk management and mitigation

No negative effects are expected on the health of users related use of the technology platform. The hardware devices used are commercial devices and CE certified and/or safety certification, the applications for older people and caregivers will be loaded on the hardware held by the users.

Technological dependence, especially on AI devices, represents a major ethical dilemma in today's society and scientific community. In order to limit the risk, the European Commission's international programmes have introduced guidelines for conducting studies that require the introduction of a new technology, called Responsible Innovation. The core principles of Responsible Innovation are also applied within the engAGE project. In particular, a strategy underlying the prevention of technological dependence is the inclusion of different actors around the older people, in the process of acquiring skills and daily use of technology. In this way, technological solutions such as those proposed by engAGE, respond to the definition of socio-technological system rather than technological, since they are placed in a care context that does not involve the replacement of the caregiver but stimulates the user to play a leading role in the management of their health.

The services proposed are intended to support the maintenance or improvement of cognitive abilities through specific activities and do not replace (in whole or in part) the support from professional services.

During the installation of the technology, moreover, information will be provided to the caregiver about the limits of the technology, which can in no way replace the role of the familiar and formal assistant, but only assist in some activities.

Users who take part in the study will not incur any direct or indirect costs related to the use of the technology platform. The platform will be provided to the subjects by the Experimental sites and must be returned to the research team at the end of the trial.

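### The field trial has informal ways to hear of harms but no record, no question asked alike in both arms and no tabulation, so it can report neither a count nor a comparison

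*Combined protocol and SAP*

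**What the plan says.** Section 5.3 of the combined protocol and SAP is the only place that says what happens when an adverse event occurs. The participant turns the device off or unplugs it, and "Participants will call the researcher, who will assist the participant in case of problems". A further bullet has the researcher come and check that nobody has been harmed. No definition, form or reporting step follows. The rule opens with "In the event of adverse events occurring despite the precautions described above (section 5.2"), but 5.2 covers technical support; the precautions are listed in 5.3 itself.

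On expected harm, 4.2 states: "No negative effects are expected on the health of users related use of the technology platform". Section 5.3 accepts that some risks exist.

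Other contact is planned. Under 5.1, "the researcher will be in contact daily with the participants", and "for all end users (including control group), they will be allowed to contact the researcher in any moment for asking information and/or assistance". Section 3.6 has formal caregivers supervise the centre sessions and the informal caregiver supervise home use. The Annex 3 interviews ask participants and both kinds of caregiver whether they felt safe and whether they see risks or negative effects of the system. Section 3.1 requires loss to follow-up and discontinuation to be noted in both groups.

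The intervention (3.6, Table 7) includes miming, dancing and yoga with balance exercises. Controls receive a booklet of home activities (3.6.1).

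**The concern.** The written procedure suits a device fault better than a fall or a strain during a physical game. It also relies on the participant to act and remember. Inclusion requires a MAC-Q of at least 25, and the plan says of that score: "A cutoff of 25 points or more indicates that the individual has a memory disorder". A control participant has no device to switch off, so the rule hardly applies to that arm.

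Two results are at stake: how many participants came to harm, and whether that differed between arms. Older people have falls and distress without any intervention, so events in the experimental arm cannot be interpreted without control-arm events collected in the same way. If neither is written down at the time, they cannot be reliably reconstructed afterwards. A report with no events would then seem to bear out the expectation in 4.2 without having tested it.

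**Working it through.** **Where a harm would have to appear.** The outcomes in 3.4 include no safety item. Tables 5 and 6 have no event row. The Annex 3 forms supplied contain no event form. The analysis in 4.1 covers description, pre/post tests, MAC-Q and correlations, with nothing on harms. By contrast, the lab test in 2.5, an interaction of about one hour, has every problem noted and reported. The field trial has no equivalent instruction.

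**What each channel delivers.**

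| Channel | Both arms? | Fixed question on events? | Dated record? | Tabulated? |
|---|---|---|---|---|
| Switch off and call (5.3) | Device-framed | No | No | No |
| Daily and open contact (5.1) | Open contact: yes; daily: not spelled out for controls | No | No | No |
| Caregiver supervision (3.6) | Experimental only | No | No | No |
| Interview items (Annex 3) | Concern the system, so not answerable by controls | Opinion, not events | No | No |
| Disposition (3.1) | Yes | Reasons not mentioned | Status only | Not stated |

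No row supplies a symmetric question, a record and a tabulation together.

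**Planned exposure.** Taking six months as 26 weeks and full adherence: home 0.5 h × 7 × 26 = 91 h; centre 1 h × 2 × 26 = 52 h; total 143 h per experimental participant. This includes dialogue and cognitive games, so it gives scale only and does not enter the bounds below.

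**Illustration of under-capture.** The plan gives no event rate, so there is no figure to reproduce. Table 2 gives 20 + 20 + 8 = 48 to 22 + 23 + 10 = 55 experimental seniors and at least 30 controls. Section 3.1 randomises 80, and 80 − 30 = 50.

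With zero recorded events, the exact one-sided 95% upper bound is 1 − 0.05^(1/n). If only a share c of events is captured, divide by c. The values of c are assumptions.

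| n | c = 1 | c = 0.5 | c = 0.25 |
|---|---|---|---|
| 48 | 6.1% | 12.1% | 24.2% |
| 50 | 5.8% | 11.6% | 23.3% |
| 55 | 5.3% | 10.6% | 21.2% |

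For 30 controls with complete capture the bound is 9.5%.

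If the true risk were 10% (assumed), the chance of recording no event among 50 is (1 − 0.10c)^50: 0.5% at c = 1, 7.7% at c = 0.5 and 28.2% at c = 0.25.

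**What a comparison could show.** With 30 against 50, a two-sided 5% test of two proportions has about 20% power for 10% against 20%, and about 55% for 10% against 30%. Even well-collected counts would be descriptive.

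**The case against.** The strongest reply is that the trial is far from blind to harms. A reader might infer that an event is noticed only if a participant telephones about a device. The documents do not support that: there is daily researcher contact, controls may make contact about anything, caregivers observe both settings, sessions end on signs of dissent (4.4), and the 5.3 visit checks people as well as equipment. All of this stands. It shows that harms may be noticed, not that they will be recorded or counted.

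A reader might also infer that a stated safety goal is left unanswered, from "security and reliability of proposed solutions" in 3.1. There the word sits beside reliability of the solutions, and 4.3 uses it for servers and access. It probably means technical security, so the point should not rest on it. Nor is there silence, since the interviews do collect views on safety and negative effects.

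EQ-5D-5L, WEMWBS, UCLA and QoL-AD are scheduled at T0 and T2, and controls are to be evaluated like the experimental group, which allows a between-arm look at deterioration. That is fair, but they measure state at two times, not events between them. Technology dependence has its own mitigation in 4.2 and 5.1.

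Section 4.4 commits to Good Clinical Practice but sets out no procedure for harms. The consent annex and Figure 2 are not in the text available, so what participants are told about risk cannot be judged.

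The objection with most practical weight concerns Norway. Section 3.2.3 says no personal medical information will be collected there and that no ethics application is needed. Section 4.3.3 excludes questions not directly connected to improving the technology. Harm questions could collide with both.

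**Conclusion.** The point holds in a limited form. Several informal channels could bring harms to light, but none is linked to a record, a question asked identically in both arms, or a tabulation. As written, the field trial can report neither a count of harms nor a between-arm comparison, despite physical and balance activities.

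The size cannot be stated from the documents. The capture shares of 50% and 25% and the 10% risk are assumptions that show only how quickly a zero loses meaning when capture is incomplete. The gap does not affect the MAC-Q analysis. It deserves correction before enrolment because the remedy is cheap and the data cannot be reliably recovered later.

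**What to change.** - Within the contact 5.1 already promises, ask the same short, neutral questions in both arms at a fixed interval and at the final visit: any fall, injury or distress since the last contact, and whether it occurred during a study activity. Ask the caregiver too where there is one. Leave out any item about losing the device, which controls cannot answer.
- Keep a dated log by subject code and arm, and record reasons for discontinuation.
- Add to 4.1 a descriptive table of counts by arm with exact intervals and no formal test.
- State the control-arm contact in 3.6.1, which now mentions only the evaluations and a first and a final meeting.
- For Norway (8–10 experimental seniors and at least 10 controls), either limit the questions to what 3.2.3 and 4.3.3 allow, with no item on unplanned medical contact, or reconcile those sections first. Report that site separately if its items differ.
- Reconcile the harm expectation in 4.2 with the risks accepted in 5.3, and correct the reference to 5.2.

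The cost is a short log, slightly more contact time and possibly an ethics or data-scope check in Norway. Clinical handling of any event is for the investigators.

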## Annex 2 – Lab testing protocols

#### SENIOR

#### RECRUITMENT PROTOCOL

Subject Identification code://						
Date of compilation:/	/					
Country of compilation:						
Name of the interviewer:						
SOCIO-DEMOGRAPHIC QUESTIONNAIRE						
Date of birth (dd /mm /yyyy)/_	/					
1. Gender: 🗆 male	□ female	🗆 dive	rse			
2. Residence:	🗆 Suburban		Rural community			
3. Housing situation:	□ Alone		Shared apartment			
With (marriage) partner	Family		□ Other:			
4. Marital status:	Single		□ widowed			

 
married / registered civil p
 
partnership
 
	partnership	□ divo	rced 🗆 solid			
5. Do you have children?	□ no	□ yes	ightarrow if yes, how much:			
6. Do you have grandchildren?	no 🗆 no	□ yes	ightarrow if yes, how much:			
7. Highest level of education:	□ No school d	egree	High school			

Secondary school	Specialized baccalaureate	Junior high school

University degree 
 Other: \_\_\_\_\_

- 8. Are you currently employed?  $\Box$  no  $\Box$  yes  $\rightarrow$  *if yes, please mark where applicable:*  $\Box$  Full-Time  $\Box$  Part-Time  $\Box$  Minijob
- 9. Are you currently retired?  $\Box$  no  $\Box$  yes  $\rightarrow$  if yes, since when: \_\_\_\_\_ (Year)
- 10. Which of the following devices do you use frequently (more than once a week)? (multiple answers possible) □ Computer □ Tablet □ Smartphone □ None
- 11. How would you rate your experience using these devices (e.g., video calling, emailing, WhatsApp) on a scale of 1 (no experience) to 5 (a lot of experience)?
  - Very little experience
     Little experience
     Not a little/not a lot
     Somewhat
     Very much

#### SYSTEM USABILITY SCALE (SUS)

	S	trongl Stro	y disa ngly a	gree - gree	>
1. I think that I would like to use this system frequently					
2. I found the system to be simple					
3. I thought the system was easy to use					
4. I think that I could use the system without the support of a technical person					
5. I found the various functions in the system were well integrated					
6. I thought there was a lot of consistency in the system					
7. I would imagine that most people would learn to use the system very quickly					
8. I found the system very intuitive					
9. I felt very confident using the system					
10. I could use the system without having to learn anything new					

#### SEMI-STRUCTURED QUESTIONNAIRE

USABILITY	

Did you find the system easy to use? If not,	
what could make it easier?	
How long did it take you to be able to use the	
system independently?	
Do you think it is necessary to have	
technological skills to be able to use the	
system to its fullest?	
Was it easy to perform the proposed exercises	
and activities?	
Was the information and commands needed	
to perform the activities easy to understand?	
Did you encounter problems while using it?	
What did you do? If the same problem	
recurred, would you be able to solve it on your	
own?	
What were the activities/features that you	
preferred? And those that you did not like?	
Could the system be improved? In what ways?	

ACCEPTANCE	
Did you enjoy using the system or did you	
perceive it as an obligation?	
Did you feel safe using the system?	
Does the product exactly match your needs? If	
not, what would you like to see added?	
Do you have concerns about privacy and the use	
of your data and personal information?	
What were the activities/features that you	
preferred? And those that you did not like?	

Do you think that continued use over time will benefit you in any way?	
Do you think there are any risks or negative effects of using the system that we have not discussed?	

WILLINGNESS TO PAY	
If the system will be launched, how should it be financed?	
How much would you pay the engAGE service per month?	
Do you think that such kind of service should be provided/payed by healthcare insurance or national healthcare system?	

